Initially, three patients will be scheduled to receive G100 at the first dose level. Dose escalation will be contingent upon acceptable safety data obtained during the first 28 days of observation following initiation of the regimen. A dose level cohort will be expanded from three to six if one of the first three patients experiences a DLT. Further patient accrual into that dose level cohort (or higher) will be suspended as soon as  $\geq 2$  patients in that cohort experience DLT, or when otherwise deemed clinically appropriate by the investigator or Sponsor medical monitor. After the 28 day DLT observation period for the final patient in a cohort is complete, if less than one third of the patients enrolled in that cohort developed a DLT, advancement to the next dose-level cohort can begin.

Patients will be considered evaluable if they have received at least three G100 injections and have completed Day 28 safety monitoring OR have experienced DLT. Patients who experienced DLT during the safety period will not be replaced. All other patients who have not received at least three G100 injections and/or do not complete the Day 28 safety monitoring period for reasons other than treatment-related toxicity will be replaced.

Following completion of the dose escalation stage of the trial, the maximum tolerated dose (MTD) or maximum safe dose (highest dose level examined in the study) will be defined as the highest dose reached in which less than one third of the patients in the cohort experienced a DLT.

In Part 2, depending on the results of Part 1 and the MTD/maximum safe dose, two groups of patients may be examined, Patient Expansion With Or Without Pembrolizumab and (optional) Large Tumor groups ([Figure 1](#)).

Part 2, Patient Expansion With or Without Pembrolizumab group: Up to 24 patients will be randomly assigned and treated with single agent intratumoral G100 ([Figure 2](#)) or with the sequential administration of intratumoral G100 and pembrolizumab ([Figure 3](#)) at the MTD or maximum safe dose of G100 determined in Part 1.

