Initially, three patients will be scheduled to receive G100 at the first dose level. Dose escalation will be contingent upon acceptable safety data obtained during the first 28 days of observation following initiation of the regimen. A dose level cohort will be expanded from three to six if one of the first three patients experiences a dose-limiting toxicity (DLT). Further patient accrual into that dose level cohort (or higher) will be suspended as soon as  $\geq 2$  patients in that cohort experience DLT, or when otherwise deemed clinically appropriate by the investigator or Sponsor Medical Monitor. After the 28-day DLT observation period for the final patient in a cohort is complete, if less than one third of the patients enrolled in that cohort developed a DLT, advancement to the next dose-level cohort can begin.

During Dose Escalation, patients will be considered evaluable for determination of safety and dose-level cohort advancement if they have received at least three complete G100 treatments and 1 dose of pembrolizumab and have completed Day 28 safety monitoring OR have experienced DLT. Patients who experienced DLT during the safety period will not be replaced. All other patients who have not received at least three G100 treatments and 1 dose of pembrolizumab and/or do not complete the Day 28 safety monitoring period for reasons other than treatment-related toxicity will be replaced.

Following completion of the Dose Escalation portion of Part 4, the maximum tolerated dose or maximum safe dose (highest dose level examined in the study) will be defined as the highest dose reached in which less than one third of the patients in the cohort experienced a DLT.

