Data from the G142 study indicate that the G100 intratumoral dose of 20 $\mu$ g is relatively safe with only grade 1 or 2 related AEs reported and no DLTs and that this higher dose appears to induce greater numbers of infiltrating CD8 T cells into the tumor. Recent preclinical data indicate that G100 doses greater than 20  $\mu$ g can lead to improved survival of animals in tumor models, further supporting that additional dose exploration may be warranted. Therefore, this arm will examine escalating doses of G100 plus rituximab in a single tumor site utilizing a 3+3 design in order to establish safety and examine clinical and biomarker responses. Once the highest safe dose/systemic exposure is determined from the Dose Escalation portion of the study, all safety, efficacy and biomarker data will be reviewed by the Sponsor (in collaboration with the independent DMC) and either the highest dose determined to be safe or the most biologically active and safe dose (if different than the MTD) will be chosen for further investigation. A Patient Expansion group would then begin. Details of Dose Escalation and Patient Expansion are described below.

*Part 5, Dose Escalation:* In the Dose Escalation portion, safety and efficacy of G100 injected into a single tumor lesion without radiation will be assessed using a 3+3 design where patients will be assigned to sequential cohorts of escalating doses of intratumoral G100 in combination with standard dose induction therapy with rituximab (Figure 8 and Figure 9). Treatment will begin on Day 0 with rituximab 375 mg/m^2 IV and continue weekly for a total of 4 doses. If there are no DLTs or significant safety events after the first dose of rituximab, G100 will be injected intratumorally beginning on Day 1, and then dosing will continue weekly for 3 additional doses (4 total) on a visit schedule that coincides with rituximab treatments as long as the tumor remains of sufficient size for injection. One lesion will be targeted to receive each dose of G100. If the lesion regresses, another lesion will be chosen for treatment. Imaging assisted injections are allowed but the feasibility and safety of these treatments must be discussed first and approved by the Medical Monitor. If the tumor lesion has not regressed completely after the first 4 doses of G100, dosing may continue for 2 additional weekly intratumoral doses (6 total). Following restaging, the patient may be eligible for a second course of G100.

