### **4.2 Safety Population**

The Safety Population includes all enrolled patients who received at least one injection of G100 after standard local radiation. Safety data analyses will be conducted on all patients in the Safety Population according to the treatment received.

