## **5.7 Safety Evaluation**

Safety evaluation will be based on safety population.

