### **5.7.2 Adverse Events**

A Treatment-Emergent Adverse Event (TEAE) is an AE with onset date on or after the initiation of study treatment, or a pre-existing condition that worsens after initiation of study treatment (i.e., increase in severity), up to 30 days after the date of last dose of study treatment. AEs that occur more than 30 days after last dose, if deemed as related to study treatment, will also be included as TEAEs.

If the AE start date is partial or missing, then:

- If AE start date is completely missing, then the AE is considered treatment-emergent.
- If both AE start month and day are missing, if the year is in the same year as the first study treatment, then the AE is considered treatment-emergent. Otherwise, 01Jan will be used to impute month and day. If the imputed AE start day is more than 30 days after the date of last study treatment, then the AE will not be a TEAE.
- If AE start day is missing and AE start year and month are the same or after the first dose year and month, then the AE is considered as treatment-emergent, unless the imputed AE start day using day 01 is more than 30 days after the date of last study drug.

The summaries will be based on TEAEs by part, treatment, and overall. A separate summary by treatment will be provided. All adverse events will be included in patient listings.

The incidence of a TEAE will be defined as the number and percent of patients experiencing an event. TEAEs will be summarized by system organ class, preferred term, and further by severity. Adverse events will be coded using Medical Dictionary for Regulatory Activities (MedDRA 20.1 or newer). A patient with more than one different adverse event in a system organ class (SOC) will be counted only once in the total number of patients experiencing adverse events in that particular SOC. A patient having experienced the same event (AE preferred term) more than once during the study will be counted only once under the worst grade or relationship.

The following adverse events summaries will be reported:

- Overall summary of TEAEs, including TEAEs, treated-related TEAEs, serious TEAEs, treatment-related serious TEAEs, TEAEs of grade 3 and above, treatment-related TEAEs of grade 3 and above, TEAEs leading to treatment interruption, TEAEs leading to treatment discontinuation, TEAEs leading to treatment interruption or discontinuation, TEAEs leading to death reported during the study, dose limiting toxicities (DLTs)

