- Incidence of TEAEs by system organ class, preferred term, and severity
- Incidence of TEAEs related to study drug by system organ class, preferred term, and severity
- Incidence of TEAEs related to G100 by system organ class, preferred term, and severity
- Incidence of TEAEs related to pembrolizumab by system organ class, preferred term, and severity
- Incidence of TEAEs related to study drug by preferred term and severity
- Incidence of TEAEs related to G100 by preferred term and severity
- Incidence of TEAEs related to pembrolizumab by preferred term and severity
- Incidence of dose limiting toxicities (DLTs) by system organ class, preferred term, and severity
- Incidence of TEAEs leading to study drug discontinuation by system organ class, preferred term, and severity
- Incidence of medical events of interest (MEOIs) by system organ class, preferred term, and severity
- Incidence of TEAEs by system organ class and preferred term
- Incidence of TEAEs related to study drug by system organ class and preferred term
- Incidence of TEAEs related to G100 by system organ class and preferred term
- Incidence of TEAEs related to pembrolizumab by system organ class and preferred term
- Incidence of serious TEAEs by system organ class and preferred term
- Incidence of serious TEAEs related to study drug by system organ class and preferred term
- Incidence of serious TEAEs related to G100 by system organ class and preferred term
- Incidence of serious TEAEs related to pembrolizumab by system organ class and preferred term
- Incidence of TEAEs leading to study drug discontinuation by system organ class and preferred term
- Incidence of TEAEs related to study drug leading to study drug discontinuation by system organ class and preferred term
- Incidence of TEAEs related to G100 leading to study drug discontinuation by system organ class and preferred term
- Incidence of TEAEs related to pembrolizumab leading to study drug discontinuation by system organ class and preferred term
- Incidence of TEAEs leading to death by system organ class and preferred term
- Incidence of TEAEs related to study drug leading to death by system organ class and preferred term

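### DLT incidence is reported on the Safety Population by part and treatment, not on the DLT-evaluable patients of each dose cohort, so the percentage can differ from the rate behind the MTD

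*SAP*

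**What the plan says.** **Reporting.** SAP 5.7 sets one population for all safety output: "Safety evaluation will be based on safety population". SAP 4.2 defines it: "The Safety Population includes all enrolled patients who received at least one injection of G100 after standard local radiation". Section 4 otherwise contains only the Enrolled and Efficacy Evaluable populations. SAP 5.7.2 lists a dedicated table, "Incidence of dose limiting toxicities (DLTs) by system organ class, preferred term, and severity", and a DLT row in the overall TEAE summary. Incidence needs a denominator: "The incidence of a TEAE will be defined as the number and percent of patients experiencing an event". The layout is also fixed: "The summaries will be based on TEAEs by part, treatment, and overall". Dose cohort is not named as a table level.

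**Dose decision.** SAP 3.1 uses a narrower group. For Part 1: "Patients will be considered evaluable if they have received at least three G100 injections and have completed Day 28 safety monitoring", or have had a DLT. For Part 4: "patients will be considered evaluable for determination of safety and dose-level cohort advancement if they have received at least three complete G100 treatments", plus one pembrolizumab dose and Day 28 monitoring, or a DLT. Part 5 asks for three G100 treatments, three rituximab doses and Day 28, or a DLT. Patients who miss these requirements for reasons other than treatment-related toxicity are replaced; patients with a DLT are not. SAP 3.4 treats the MTD as exceeded at two or more DLTs in a cohort and defines the MTD as the highest dose with a cohort rate below one third.

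**Part 5 sequence.** Rituximab comes first, on Day 0. Then: "If there are no DLTs or significant safety events after the first dose of rituximab, G100 will be injected intratumorally beginning on Day 1". Protocol 6.2 counts toxicity related to any study component, rituximab included, as a possible DLT.

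**The concern.** A reader of the study report should be able to go from the DLT table to the MTD. Two features of the plan can prevent this.

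- **Denominator.** A patient who received one or two G100 injections and then left for a reason unrelated to toxicity is replaced for escalation but stays in the Safety Population. That patient adds to the denominator without having been observed for DLT through Day 28.
- **Numerator.** In Part 5, a patient with a DLT after Day 0 rituximab is evaluable and is not replaced. If no G100 is ever given, the patient fails the G100 requirement of SAP 4.2 and is missing from the DLT table and from every other adverse event table.

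Relative to the rate used for escalation, both effects lower the reported percentage. A third feature hides the comparison: a table by part and treatment need not show any cohort's rate.

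**Working it through.** **1. The plan's own rule (SAP 3.4).** On evaluable denominators the count rule and the one-third rule agree:

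- 1/6 = 16.7%, below 33.3%: escalation may proceed.
- 2/6 = 33.3%, 2/5 = 40.0%, 2/4 = 50.0%, 2/3 = 66.7%: none is below one third, and each is a cohort with two DLTs.

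**2. Adding replaced patients.** Let n be the evaluable patients in a cohort and k the replaced patients who had at least one G100 injection. The Safety Population rate is d/(n + k). With d = 2, it falls below one third when n + k is 7 or more. The documents give no value for k, so every k here is an assumption.

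| Evaluable result | Smallest k that takes the rate below one third | Rate shown |
|---|---|---|
| 2/6 = 33.3% | 1 | 2/7 = 28.6% |
| 2/5 = 40.0% | 2 | 2/7 = 28.6% |
| 2/4 = 50.0% | 3 | 2/7 = 28.6% |
| 2/3 = 66.7% | 4 | 2/7 = 28.6% |

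For the full cohort of six, k = 2 gives 2/8 = 25.0% and k = 3 gives 2/9 = 22.2%. A cohort that passes is affected too: 1/6 = 16.7% becomes 1/8 = 12.5% with k = 2.

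**3. Part 5 numerator.** Take six evaluable patients with two DLTs, one of them after Day 0 rituximab in a patient who never receives G100. Escalation sees 2/6 = 33.3%. The Safety Population has five of the six patients and one of the two DLTs: 1/5 = 20.0%.

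**4. How often the one-third line would be crossed.** A 3+3 cohort with replacement was simulated, 60,000 cohorts per setting. Assumptions: 5% to 30% of patients without a DLT are dosed but not evaluable, and results are shown by cohort. Entries are the share of cohorts with two or more DLTs whose Safety Population rate is below one third.

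| True DLT rate | Accrual stops at the second DLT | Each group of three is filled first |
|---|---|---|
| 20% | 4.2% to 25.1% | 10.6% to 38.3% |
| 33% | 2.4% to 14.5% | 6.4% to 20.9% |
| 50% | 0.8% to 4.9% | 2.3% to 6.8% |

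**5. The Safety Population definition.** SAP 4.2 requires G100 given after local radiation. Parts 4 and 5 omit radiation (Protocol 8.3), so read literally no Part 4 or Part 5 patient qualifies. The Part 4 and 5 fractions above assume that this clause is ignored. Protocol 14.3.1 is wider: it admits anyone given study drug by injection or who undergoes a study procedure. Protocol 4.7 describes the safety data set by G100 injection alone. SAP section 9 does not list the narrower definition as a change from Protocol 14.3.1.

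**The case against.** The strongest reply is that nothing in the conduct of the trial depends on this table. Exceeding the MTD is decided by counting two DLTs, and a table with two DLTs still shows two, whatever the denominator. A reader might infer that the SAP could reverse or bias an escalation decision; the documents do not support that. The reply stands, except that the Part 5 Day 0 case can remove a DLT from the count itself.

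Further points:

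- **Cohort rates are not a specified output.** A reader might infer that the planned table would directly contradict the MTD. That needs a cohort-level table, which SAP 5.7.2 does not name. The fractions above assume one.
- **The denominator of the dose rule is not settled.** The advancement rule in SAP 3.1 refers to patients enrolled in the cohort, and the MTD definition to patients in the cohort. The evaluable basis comes from the evaluability and replacement paragraphs. This is a reasonable reading, but an inference.
- **The evaluable rate is not an unbiased reference.** It keeps a partly observed patient who has a DLT and drops one who does not. Assume a true rate of 20%, 10% uniform dropout and uniform DLT timing. Observed DLTs are 0.20 × (0.90 + 0.10 × 0.5) = 0.19, and unobserved dropouts are 0.10 × (1 − 0.20 × 0.5) = 0.09. All dosed patients then give 19.0% and evaluable patients 0.19/0.91 = 20.9%. The case for the evaluable set is that it matches the decision, not that it estimates the true risk better.
- **The DLT rate is not the primary endpoint.** That is the nature, frequency and severity of adverse events, with response frequency added in Parts 4 and 5 (Protocol 5.4). Protocol 14.3.1 asks for DLT listings, and SAP 5.7.2 lists all adverse events.
- **The practical exposure may be small.** SAP 3.1 reports no DLTs at 20 µg, the highest dose in Parts 1 to 3, so that rate is zero on either denominator. SAP section 9 records termination of the study, and the SAP names no rituximab-specific tables. Protocol 6.5 also allows further G100 after a DLT case by case, so a Day 0 DLT does not always mean no G100.

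These points limit the consequence. They do not supply the missing population or remove replaced patients from the denominator.

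**Conclusion.** The point holds as a reporting defect. Followed as written, SAP 5.7 and 5.7.2 give a DLT percentage on a different group from the one SAP 3.1 uses for escalation, and at a level that need not show the dose cohort.

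One replaced patient is enough to turn 33.3% into 28.6% in a cohort with 2 DLTs in 6 evaluable patients. One Part 5 Day 0 DLT without G100 can turn 33.3% into 20.0%. Both figures assume cohort-level display and that the radiation clause of SAP 4.2 is not applied to Parts 4 and 5. The actual size depends on the number of replaced patients, which the documents do not give. With no replaced patients and no Day 0 event, the cohort rates agree.

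The documents do not support the stronger conclusions that escalation decisions are affected or that a main result of the trial is biased. The correction is worth making because it is cheap and lets the report reproduce its own MTD.

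**What to change.** 1. Add a DLT-evaluable population to SAP section 4, using the part-specific definitions already in SAP 3.1. Produce the DLT table on it by part and dose cohort, with the Safety Population version as supportive. Other adverse event tables stay on the Safety Population.
2. Correct SAP 4.2 in line with Protocol 14.3.1: drop the radiation condition for Parts 4 and 5, and include patients who received any study drug. A Part 5 patient given only rituximab is then kept in all adverse event tables. Align Protocol 4.7, or record the difference in SAP section 9. Step 1 alone would not repair the other adverse event tables.
3. Reconcile the advancement wording, which refers to enrolled patients, with the evaluability and replacement paragraphs, so that the denominator of the one-third rule is stated once.

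This is a free improvement: one new population definition, one corrected definition, one reconciled sentence and one changed table. It needs no additional patients or data collection.

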### **5.7.1 Treatment Exposure**

Local radiation therapy received will be summarized by frequency. Number of radiation doses (for Part 1, 2, and 3), number of G100 doses in first course, number of G100 doses modification in first course, number of G100 doses in second course, number of G100 doses modification in second course, cumulative pembrolizumab dose (mg), treatment duration of pembrolizumab (weeks), and number of pembrolizumab infusion interruptions will be reported.

Treatment duration of pembrolizumab (weeks) will be calculated as (date of last pembrolizumab dose administered – date of first pembrolizumab dose administered + 21) / 7. Pembrolizumab treatment interruption, if any, will be removed from treatment duration of pembrolizumab.

In addition, duration from first course to second course in month, calculated as (first dose date of G100 in second course – last dose date of G100 in first course + 1)/30.4375, will be reported. Treatment site for irradiated lesions, type of imaging used for G100 injection will be reported.

G100, pembrolizumab administration, and low dose radiation treatment (Part 1, 2, and 3) will be displayed in listings.

### **5.7.2 Adverse Events**

A Treatment-Emergent Adverse Event (TEAE) is an AE with onset date on or after the initiation of study treatment, or a pre-existing condition that worsens after initiation of study treatment (i.e., increase in severity), up to 30 days after the date of last dose of study treatment. AEs that occur more than 30 days after last dose, if deemed as related to study treatment, will also be included as TEAEs.

If the AE start date is partial or missing, then:

- If AE start date is completely missing, then the AE is considered treatment-emergent.
- If both AE start month and day are missing, if the year is in the same year as the first study treatment, then the AE is considered treatment-emergent. Otherwise, 01Jan will be used to impute month and day. If the imputed AE start day is more than 30 days after the date of last study treatment, then the AE will not be a TEAE.
- If AE start day is missing and AE start year and month are the same or after the first dose year and month, then the AE is considered as treatment-emergent, unless the imputed AE start day using day 01 is more than 30 days after the date of last study drug.

The summaries will be based on TEAEs by part, treatment, and overall. A separate summary by treatment will be provided. All adverse events will be included in patient listings.

The incidence of a TEAE will be defined as the number and percent of patients experiencing an event. TEAEs will be summarized by system organ class, preferred term, and further by severity. Adverse events will be coded using Medical Dictionary for Regulatory Activities (MedDRA 20.1 or newer). A patient with more than one different adverse event in a system organ class (SOC) will be counted only once in the total number of patients experiencing adverse events in that particular SOC. A patient having experienced the same event (AE preferred term) more than once during the study will be counted only once under the worst grade or relationship.

The following adverse events summaries will be reported:

- Overall summary of TEAEs, including TEAEs, treated-related TEAEs, serious TEAEs, treatment-related serious TEAEs, TEAEs of grade 3 and above, treatment-related TEAEs of grade 3 and above, TEAEs leading to treatment interruption, TEAEs leading to treatment discontinuation, TEAEs leading to treatment interruption or discontinuation, TEAEs leading to death reported during the study, dose limiting toxicities (DLTs)
- Incidence of TEAEs by system organ class, preferred term, and severity
- Incidence of TEAEs related to study drug by system organ class, preferred term, and severity
- Incidence of TEAEs related to G100 by system organ class, preferred term, and severity
- Incidence of TEAEs related to pembrolizumab by system organ class, preferred term, and severity
- Incidence of TEAEs related to study drug by preferred term and severity
- Incidence of TEAEs related to G100 by preferred term and severity
- Incidence of TEAEs related to pembrolizumab by preferred term and severity
- Incidence of dose limiting toxicities (DLTs) by system organ class, preferred term, and severity
- Incidence of TEAEs leading to study drug discontinuation by system organ class, preferred term, and severity
- Incidence of medical events of interest (MEOIs) by system organ class, preferred term, and severity
- Incidence of TEAEs by system organ class and preferred term
- Incidence of TEAEs related to study drug by system organ class and preferred term
- Incidence of TEAEs related to G100 by system organ class and preferred term
- Incidence of TEAEs related to pembrolizumab by system organ class and preferred term
- Incidence of serious TEAEs by system organ class and preferred term
- Incidence of serious TEAEs related to study drug by system organ class and preferred term
- Incidence of serious TEAEs related to G100 by system organ class and preferred term
- Incidence of serious TEAEs related to pembrolizumab by system organ class and preferred term
- Incidence of TEAEs leading to study drug discontinuation by system organ class and preferred term
- Incidence of TEAEs related to study drug leading to study drug discontinuation by system organ class and preferred term
- Incidence of TEAEs related to G100 leading to study drug discontinuation by system organ class and preferred term
- Incidence of TEAEs related to pembrolizumab leading to study drug discontinuation by system organ class and preferred term
- Incidence of TEAEs leading to death by system organ class and preferred term
- Incidence of TEAEs related to study drug leading to death by system organ class and preferred term

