5.4 Primary Endpoint

- Part 1: The nature, frequency and severity of AEs and laboratory abnormalities up through Study Day 28 in patients with low-grade NHL receiving intratumoral G100 and local radiation
- Part 2: The nature, frequency and severity of AEs and laboratory abnormalities occurring in patients with follicular NHL receiving local radiation and either intratumoral G100 alone or sequential intratumoral G100 and anti-PD-1 therapy
- Part 3: The nature, frequency, and severity of AEs and laboratory abnormalities occurring in patients with follicular NHL receiving local radiation and G100 at 20 µg/dose
- Part 4: The nature, frequency and severity of AEs and laboratory abnormalities and the frequency of clinical responses occurring in patients with follicular NHL receiving intratumoral G100 at 20 µg/lesion in single or multiple tumor masses and pembrolizumab therapy
- Part 5: The nature, frequency and severity of AEs and laboratory abnormalities and the frequency of clinical responses occurring in patients with follicular NHL receiving rituximab therapy in combination with escalating doses of intratumoral G100 in single tumor lesions

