5.5 Secondary Endpoints

- The nature, frequency and severity of AEs and laboratory abnormalities until 21 days after G100 regimen is completed or discontinued

- Clinical responses by irRC using bi-dimensional measurements and expressed as PR, CR, SD, or PD, and TTP and/or progression-free survival (PFS) as a preliminary indication of efficacy
- As an exploratory comparison, assess clinical responses by the International Working Group response criteria for lymphomas. (For determining PD, the irRC criteria will be used.) Sponsor will assess for clinical responses by the Lugano criteria for lymphomas ([Cheson 2014](#)).
- Abscopal tumor responses in non-treated, distal tumor sites

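### No planned safety summary yields the protocol's Day 28 (Part 1 primary) or 21-day (secondary) endpoint, and the Part 2 arms are shown as crude percentages over unequal windows

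*SAP*

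**What the plan says.** Protocol 5.4 defines the Part 1 primary endpoint as "The nature, frequency and severity of AEs and laboratory abnormalities up through Study Day 28 in patients with low-grade NHL" treated with G100 and local radiation. The Part 2 primary endpoint in the same section has no time limit. The first secondary endpoint, in Protocol 5.5, is "The nature, frequency and severity of AEs and laboratory abnormalities until 21 days after G100 regimen is completed or discontinued".

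SAP 5.7.2 uses one window. A treatment-emergent AE (TEAE) starts or worsens on or after the start of study treatment, "up to 30 days after the date of last dose of study treatment". The next sentence extends this: "AEs that occur more than 30 days after last dose, if deemed as related to study treatment, will also be included as TEAEs". The section then states "The summaries will be based on TEAEs by part, treatment, and overall", and "The incidence of a TEAE will be defined as the number and percent of patients experiencing an event". Events outside the window appear only as listings: "All adverse events will be included in patient listings".

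SAP 5.7.4 tabulates laboratory values by visit and cross-tabulates baseline grade against the worst later grade, with no end date. SAP section 9, which records departures from the protocol's planned analysis, mentions neither safety window.

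**The concern.** Two safety endpoints have a stated period in the protocol, and one of them is the primary endpoint of Part 1. If the SAP is followed as written, no AE or laboratory-grade summary will be cut at either period. The Part 1 primary question would be answered with events from a longer span, and nothing in the SAP says the endpoint was changed.

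The same window creates a second difficulty in Part 2. Follow-up for TEAEs ends soon after G100 in the G100-alone arm, but can continue for up to two years of pembrolizumab in the other. With incidence reported as a crude percentage, the pembrolizumab arm would tend to show more patients with events even if the underlying rates were equal.

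**Working it through.** The documents give no figure for this point to reproduce; the check is calendar arithmetic.

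**Inputs**
- G100 dose 6 on Day 35 and optional dose 9 on Day 56 (Protocol 10.3.6 and 10.3.8).
- Pembrolizumab from Day 14, every 21 days, for up to two years (SAP 3.1).
- Second G100 course no sooner than 6 weeks (42 days) after the first (SAP 3.1).
- Lengths are counted inclusively from Day 0.

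**One G100 course, G100 alone**

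| | 6 doses | 9 doses |
|---|---|---|
| SAP window end (last dose + 30) | 35 + 30 = Day 65 | 56 + 30 = Day 86 |
| Secondary endpoint end (last dose + 21) | 35 + 21 = Day 56 | 56 + 21 = Day 77 |
| SAP window length | 66 days | 87 days |
| Ratio to the 29-day Part 1 primary window | 66/29 = 2.3 | 87/29 = 3.0 |

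**Earliest second course**
- 6 + 6 doses: 35 + 42 + 35 = Day 112, window to Day 142.
- 9 + 9 doses: 56 + 42 + 56 = Day 154, window to Day 184 (185 days).

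**Pembrolizumab arm, Part 2**
- Full two years: 14 + 34 × 21 = Day 728 (35 doses), window to Day 758 (759 days). Ratios to one G100 course: 759/87 = 8.7 and 759/66 = 11.5. Against a 9 + 9 second course: 759/185 = 4.1.
- Stopping after 8 doses: 14 + 7 × 21 = Day 161, window to Day 191 (192 days). Ratios: 192/87 = 2.2 and 192/66 = 2.9. Against a 9 + 9 second course: 192/185 = 1.04.

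**Illustration of the effect on crude percentages.** Assume the same constant AE rate in both arms; this rate is not in the documents. P(at least one AE) = 1 − exp(−rate × days/365.25), for 66 versus 759 days:
- 0.25 per year: 4.4% versus 40.5%
- 0.5 per year: 8.6% versus 64.6%
- 1 per year: 16.5% versus 87.5%

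**Does any other planned output supply the endpoints?**
- DLT tables (SAP 5.7.2): DLTs are limited to the first 28 days, but only to at-least-possibly-related events on a defined list (Protocol 6.2). The endpoint covers all AEs.
- AE listings: they would allow a later derivation but are not a planned summary.
- Laboratory data (SAP 5.7.4): the text names Visits 2, 10 and 11, whereas Day 28 is Visit 9 in the Part 1 schedule. By-visit means do not show abnormalities accumulated through Day 28, and the shift tables have no cut-off.

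**Side finding.** For patients without pembrolizumab, Protocol 12.4 collects all AEs to the later of the end-of-study visit (Day 77) and 30 days after the last dose. After six doses the SAP window stops at Day 65, so unrelated AEs on Days 66 to 77 are collected and listed but not summarised.

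**The case against.** The strongest reply is that the SAP follows other parts of the protocol. Protocol 14.3.1 asks for the highest grade per patient and the number and percentage with AEs, with no cut at Day 28 or 21 days. Protocol 14.4 takes the Part 1 interim data through Day 77. On this view the misalignment begins inside the protocol. That is fair as to its origin, but sections 5.4 and 5.5 still define the endpoints, and neither document withdraws them.

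A second reply is that, with one course of G100 alone, the SAP window contains both protocol windows and exceeds the 21-day one by only 9 days. This stands: the effect is over-inclusion. A reader might infer that events inside the protocol windows are lost; the documents do not support that.

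Third, a reader might infer that the Part 2 analysis departs from its primary endpoint. It does not. That endpoint states no window, and Protocol 12.0 and 12.4 collect AEs to 30 days after pembrolizumab stops. Part 2 is exploratory, no safety hypothesis is tested, pembrolizumab duration is reported (SAP 5.7.1), and events related to each drug are tabulated separately. These points reduce the concern to one of comparability. They do not remove it, because Protocol 14.1 intends direct comparison between groups where possible and no exposure adjustment is planned.

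Finally, Part 1 has at most 12 evaluable patients, so Day 28 events could be picked out of the listings by hand. That makes the remedy easy, but it does not make it planned.

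**Conclusion.** The point holds: the Part 1 primary safety endpoint and the 21-day secondary safety endpoint have no planned summary, and the SAP records no change. For Part 1 the reported window would be 2.3 to 3.0 times the stated one with a single course, and longer with a second. This should be corrected before the tables are run.

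In Part 2 the issue is unequal time at risk under crude percentages. The size depends on how long pembrolizumab is actually given: 8.7- to 11.5-fold is the ceiling, 2.2- to 2.9-fold applies if it stops after eight doses, and the gap narrows further with a second G100 course. Adding two full years to Day 14 would suggest a window to Day 774 (14 + 730 + 30), but three-weekly dosing puts the last dose on Day 728 and the window end on Day 758.

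Two further readings go too far. AE summaries are not restricted to 30 days after the last dose, because later related events are added; this widens the mismatch. Nor is the SAP without any 28-day output, since the DLT table is one.

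The figures assume dosing on schedule, a count from Day 0, and that the last dose of study treatment means the last dose of any agent in any course. The SAP does not define that term by agent, so this last assumption is an inference.

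**What to change.** In SAP 5.7.2 and 5.7.4:

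1. Add Part 1 AE and laboratory-grade tables restricted to onset through Day 28, designated as the primary safety analysis.
2. Add AE and laboratory-grade tables for all parts cut at 21 days after the last G100 dose, stating whether the G100 regimen means the first course only or includes a second.
3. Define the last dose of study treatment by agent and course.
4. For side-by-side display of the Part 2 arms, use the common 21-day cut or exposure-adjusted rates.
5. Keep the 30-day TEAE tables as supportive.

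If either endpoint is deliberately dropped, record that and the reason in SAP section 9. The cost is a few repeated tables and some SAP wording. Safety is descriptive, so no error rate or power is affected, and no new data are needed.
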